7.8. General Considerations for Efficacy during Maintenance Period

The Maintenance Period starts after the first injection of study treatment at Week 16 and ends after last injection of study treatment at Week 52.

Baseline for the Maintenance Period analyses will be the same as that for the Induction Period. See Section 7.2.4 for discussion on derivation of baseline.

This document is confidential.

All efficacy and QoL variables for the Maintenance Period will be analysed by means of descriptive statistics presented by treatment group as randomised during the Induction Period.

7.9. Control for multiplicity

In the study there is no control for the overall type one error, only the primary endpoint needs to be statistically significant in order the study to be a success. Thus, no control for multiplicity approach is defined.

This document is confidential.

8. Demographic, Other Baseline Characteristics and Medication

8.1. Patient Disposition and Withdrawals

The number of patients included in each analysis set will be summarised using descriptive statistics by study period and treatment group based on the Enrolled Subjects. The reasons for exclusion will be presented in the listings of protocol deviations, and in the Blind Data Review Meeting report. In addition, patients completed treatment and discontinued, together with the reasons for discontinuation within each study period and follow-up will also be summarised by study period and treatment group based on FAS. Similarly, patients completed study and discontinued, together with the reasons for discontinuation will be summarized.

8.2. Protocol Deviations

Protocol deviations will be summarized descriptively for patients with at least 1 important protocol deviation and patients with at least 1 non-important protocol deviation for each treatment group and overall. Each protocol deviation will also be summarized descriptively within important and non-important protocol deviations for each treatment group and overall of the FAS. A patient can have multiple important and/or non-important deviations and counted once per important and/or non-important deviation. COVID-19-related protocol deviations will be summarized descriptively for each treatment group and overall of the FAS.

A listing of protocol deviations, including COVID-19-related protocol deviations, will be provided.

8.3. Demographic and Baseline Characteristics

The following demographic and baseline characteristics will be analysed by treatment group based on the FAS:

- Age (in years)
- Age group (Adolescents <=12 to <18 Years ; Adults >=18 Years)
- Sex (Male; Female)
- Ethnicity (Hispanic or Latino; Not Hispanic or Latino; Not Reported; Unknown)
- Race (White; Black or African American; American Indian or Alaska Native; Asian; Native Hawaiian or Other Pacific Islander; Other; Not Reported)
- Fitzpatrick Skin Type (I; II; III; IV; V; VI)
- Height (in cm)
- Weight (in kg)
- Body Mass Index (BMI (kg/m²) = Weight(kg)/[Height(m)²])
- Body Mass Index (BMI) categories (Underweight / normal weight/ overweight/ obesity)
- Prior use of dupilumab (Yes/No)
- Baseline disease severity: (IGA=3 / IGA=4)

This document is confidential.

- AD duration (based on AD onset, years)

8.4. Medical History and Concomitant Diseases

Medical history information, as recorded in eCRF, will be listed on the SAF.

Medical histories are defined as the conditions/events recorded on the *Medical History* electronic case report form (eCRF) with a start date prior to the first study drug injection.

The number and percentage of patients with medical histories will be summarized for the SAF Population by treatment group using the MedDRA Preferred Term (PT) nested within System Organ Class (SOC), MedDRA version 24.1 or higher.

8.5. Other Baseline Characteristics

Atopic Dermatitis History, Serology, Coagulation, and WOCBP as recorded on the eCRF will only be presented in data listings on the SAF.

8.6. Medication

Medications/procedures will be coded using the latest version of the WHO Drug dictionary. The dictionary version used will be specified in the data display footnote. Imputation of missing and partial dates, for the purpose of assigning prior/concomitant status is described in [Section 7.3.3](#).

8.6.1. Prior Medication

Medications/procedures that start prior to the date of first dose and stop prior to or on the date of first dose of study drug are considered prior medications/procedures. Prior medications will be summarized by treatment group and also presented in data listings on the SAF.

8.6.2. Concomitant Medication

Concomitant medications/procedures are those medications that start before, on, or after the first day of study treatment of the defined treatment period and continue into the treatment period. Concomitant medications are assigned to the treatment period in which they are actually ongoing. For example, if a patient is receiving a concomitant medication during the Induction Period but has a stop date during the Induction Period, the same medication would not be listed as a concomitant medication during the Maintenance Period unless patient has a new start date.

Patient incidence will be tabulated for the concomitant medications/procedures by Anatomic Therapeutic Class (ATC) and preferred term for all patients in the FAS, by treatment group and overall. Tables will be sorted by descending frequency of ATC level 2 and descending frequency of preferred term within the ATC level. Patients will be counted only once for each ATC and each preferred term in the event that they have multiple records of the same ATC or preferred term in the database. All concomitant medications/procedures will be presented in data listings.

8.6.3. Post Medication

Once the last dose of study drug is taken (i.e., the last visit at which the patient takes study drug) and related trial measurements are completed, patients should continue to take their usual medications, also allowed during the trial, and may resume other medications that were interrupted before trial enrolment as deemed appropriate by the Investigator. The study drug is for experimental use only, and there are other therapies available to treat the disease.

This document is confidential.

Only concomitant medication associated with adverse events will be captured between the last study drug administration and last phone contact/visit (i.e., safety follow-up).

Post medications will be flagged in concomitant medication listings.

8.6.4. Rescue Medication

Rescue medications during the Induction Period and Maintenance Blinded Period will be presented by treatment group for the FAS Population. The use of systemic corticosteroids for the treatment of AD is prohibited and requires permanent discontinuation of the Investigational Product. If a systemic corticosteroid is used for the treatment of AEs (eg, worsening of existing condition, such as asthma exacerbation), it will be treated as rescue medication.

The use of rescue medications identified as an ICE will be summarized under the efficacy analyses of [Section 9.3](#).

8.7. Extent of Exposure

Total drug exposure (in mg) is defined as the total investigational product in mg that was taken during the study.

Total exposure duration to investigational product (in days) is defined as: Date of last dose – date of first dose + 1. Note that this does not exclude days when the dose has been missed.

Percent of the planned exposure received is defined as the total drug exposure, divided by planned exposure, times 100.

For patients in the lebrikizumab arm,

- Patients who complete the Induction Period, planned exposure is 16 weeks of treatment planned, with a total dose equal to $2*500\text{mg} + 7*250\text{mg} = 2750\text{mg}$
- Patients who complete the Maintenance Period, planned exposure is 35 weeks of treatment planned, with a total dose equal to $250\text{mg} * 17 = 4250\text{mg}$
- German extension: total dose (in mg) is calculated by the number of active injections taken during the treatment period multiplied by dose.

For patients in the placebo arm,

- Patients who complete the Induction Period, planned exposure is the loading dose at week 16, with a total dose equal to $2*250\text{mg} = 500\text{mg}$
- Patients who complete the Maintenance Period, planned exposure is 35 weeks of treatment planned, with a total dose equal to $2*250\text{mg} + 250\text{mg} * 16 = 4500\text{mg}$
- German extension: total dose (in mg) is calculated by the number of active injections taken during the treatment period multiplied by dose.

Finally, the total exposure in patient years will be calculated as:

$$\text{Total exposure in patient years} = \frac{\text{Sum of duration of exposures for all patients in treatment group}}{365.25}$$

This document is confidential.

Total drug exposure, total exposure duration, total exposure in patient years, and percent of the planned exposure received will be summarized using the SAF and actual treatment group for each period.

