7.7. General Considerations for Efficacy during Induction Period

The Induction Period starts after the first injection of study treatment at Baseline Visit (Day 1) and ends prior to the first injection of study treatment at Week 16 or the early termination visit (ETV) (between Day 1 and Week 16). For patients who are randomized but not dosed, the Induction Period starts on the date of randomization.

For Pruritus Numeric Rating Scale (NRS) and Sleep-Loss due to Pruritus collected via eDiary, the baseline period is the 7-day window prior to the first injection. A patient must have responses on at least 4 of 7 days to calculate a baseline weekly mean. If a patient has 3 or fewer responses, the baseline mean value will be considered missing.

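### SAP 8.7 counts the Week 16 injection as Induction exposure, while SAP 7.7, SAP 4.1.3 and the protocol's dosing table place it in Maintenance

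*SAP*

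**What the plan says.** SAP 8.7 sets planned exposure by arm and period. For the lebrikizumab arm it gives 2 × 500 + 7 × 250 = 2750 mg in Induction and 17 × 250 = 4250 mg in Maintenance. For the placebo arm, "planned exposure is the loading dose at week 16" in Induction (500 mg), and Maintenance is 2 × 250 + 16 × 250 = 4500 mg. For Maintenance in both arms it adds that "planned exposure is 35 weeks of treatment planned". Percentage of plan is total drug taken divided by planned exposure, times 100. It is reported by period and actual treatment group on the safety set, together with exposure duration and patient-years. Total drug taken is defined over the study as a whole.

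The period boundaries are given elsewhere. SAP 7.7 says that Induction "ends prior to the first injection of study treatment at Week 16". SAP 7.8 says: "The Maintenance Period starts after the first injection of study treatment at Week 16". SAP 4.1.3, which covers Maintenance from Week 16 to Week 52, describes the Week 16 and Week 18 injections there. Protocol 7.1 does the same in Table 4, the dosing schedule for Maintenance, and Protocol 7.2.3 assigns the placebo arm's Week 16 and Week 18 loading doses to Maintenance.

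**The concern.** The planned figures in 8.7 use one period boundary and the rest of the plan uses another. The percentage of plan needs a numerator and a denominator cut at the same point, and 8.7 does not say how actual doses are assigned to periods. Two programmers could follow the SAP in good faith and produce different tables. One table would make full dosing look like under-dosing in Induction and over-dosing in Maintenance. The other would list active drug as placebo-arm exposure in the only placebo-controlled period, which SAP 10 labels simply as lebrikizumab versus placebo. These tables are the background against which the by-period safety results are read.

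**Working it through.** **Inputs.** Dosing is every 2 weeks from Week 0, with the last dose at Week 50 (SAP 4.1, 4.5), so there are 26 dosing visits. The lebrikizumab arm has 500 mg at Weeks 0 and 2 and 250 mg at every later visit. The placebo arm has no lebrikizumab before Week 16, 500 mg at Weeks 16 and 18, and 250 mg from Week 20 (SAP 4.1.3; Protocol Table 4).

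**Step 1: reproduce the SAP 8.7 figures.** They come out exactly if the Week 16 dose is counted in Induction:

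- Lebrikizumab, Weeks 0 to 16: 2 × 500 + 7 × 250 = 2750 mg. The seven doses are Weeks 4, 6, 8, 10, 12, 14 and 16.
- Lebrikizumab, Weeks 18 to 50: 17 × 250 = 4250 mg.
- Placebo arm, Week 16: 2 × 250 = 500 mg.
- Placebo arm, Weeks 18 to 50: 500 + 16 × 250 = 4500 mg.

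**Step 2: recount with the SAP 7.7 boundary**, putting the Week 16 dose in Maintenance:

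- Lebrikizumab, Weeks 0 to 14: 2 × 500 + 6 × 250 = 2500 mg; Weeks 16 to 50: 18 × 250 = 4500 mg.
- Placebo arm, Weeks 0 to 14: 0 mg; Weeks 16 to 50: 2 × 500 + 16 × 250 = 5000 mg.

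Whole-study totals agree under both splits: 2750 + 4250 = 2500 + 4500 = 7000 mg, and 500 + 4500 = 0 + 5000 = 5000 mg. Only the allocation between periods differs.

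**Step 3: percentage of plan for a fully dosed patient**, with the denominator from 8.7:

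| Arm and period | Actual doses cut by SAP 7.7 | Actual doses cut as in 8.7 |
|---|---|---|
| Lebrikizumab, Induction | 2500/2750 = 90.9% | 2750/2750 = 100% |
| Lebrikizumab, Maintenance | 4500/4250 = 105.9% | 4250/4250 = 100% |
| Placebo arm, Induction | 0/500 = 0% | 500/500 = 100% |
| Placebo arm, Maintenance | 5000/4500 = 111.1% | 4500/4500 = 100% |

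The right-hand column is consistent, but its third row rests on 500 mg of lebrikizumab counted as placebo-arm Induction exposure.

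**Step 4: duration.** SAP 8.7 defines duration as last dose minus first dose plus 1. If it is cut by period, a lebrikizumab-arm patient dosed on nominal dates has 14 × 7 + 1 = 99 Induction days with the last dose at Week 14, or 16 × 7 + 1 = 113 days with the last dose at Week 16. The second is about 14% longer (113/99 = 1.14), and patient-years move with it.

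**Step 5: the 35-week label.** Week 16 to Week 52 is 36 weeks and Week 18 to Week 52 is 34. The stated 35 matches neither.

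**The case against.** The best defence is that 8.7 is consistent within itself. Its sums are correct, its two periods add up to the right totals, and it names the Week 16 dose openly. A programmer who assigned actual doses in the same way would get 100% throughout. SAP 7.7 and 7.8 stand under efficacy headings, SAP 10 defines safety periods only as up to Week 16 and from Week 16 on, and the schedule of assessments lists the Week 16 administration in its Induction table.

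Much of this stands. It limits the consequence and probably explains where the 8.7 split came from. It does not remove the conflict. SAP 4.1.3 and Protocol Table 4 are not efficacy text. The schedule's own footnote places the Week 16 loading doses in Maintenance. And 8.7 states no rule for the per-period numerator.

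Four stronger readings might be inferred, and the documents do not support them:

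- That the tables will necessarily show 90.9% and 0%. Those figures require actual doses to be cut by 7.7 and the plan by 8.7, a combination the SAP permits but does not prescribe.
- That the Week 16 injection belongs to neither period, because 7.8 starts Maintenance after it. This is over-literal: 7.7 also starts Induction after the Baseline injection. The same reading would drop the Day 1 dose and give 2000/2750 = 72.7%.
- That the 35-week label distorts the results. Percentage of plan is computed in mg, so the label enters no formula.
- That placebo patients are given lebrikizumab during the controlled comparison. The question is which period the dose is booked to; no dosing error is shown.

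**Conclusion.** The inconsistency is real. SAP 8.7 books the Week 16 injection to Induction in both arms, and SAP 7.7, SAP 4.1.3 and the protocol place it in Maintenance. The amount misallocated is 250 mg per fully dosed lebrikizumab patient and 500 mg per placebo-arm patient. Which symptom appears depends on how actual doses are assigned: percentages of plan away from 100%, or 500 mg of active drug in the placebo arm's Induction summary. The 500 mg stands in the placebo arm's Induction plan either way.

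The figures assume that every scheduled dose is given at its scheduled visit. The effect is limited to the descriptive by-period exposure tables; whole-study exposure, the primary analysis and the other efficacy analyses are untouched. It should be corrected because it is cheap to do and the tables would otherwise mislead, but it does not threaten the trial's conclusions.

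**What to change.** Reconcile SAP 4.1.3, 7.7, 7.8 and 8.7 so that the Week 16 injection is counted in one period, for planned and actual exposure alike. This is bookkeeping on the existing schedule and changes no dose.

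- With the SAP 7.7 boundary, restate planned exposure in 8.7 as Induction 2500 mg (lebrikizumab arm) and 0 mg (placebo arm), and Maintenance 4500 mg and 5000 mg.
- Reword 7.8 so that Maintenance begins with the Week 16 injection. The same section refers to a last injection at Week 52, while SAP 4.1 gives the last dose at Week 50; these also need to be reconciled.
- State in 8.7 that the per-period numerator, duration and patient-years use this boundary.
- Show the placebo arm's Induction percentage of plan as not applicable, since it becomes 0/0.
- Change the 35-week label to the 36-week Maintenance Period.

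The cost is four figures, one label and a few sentences in the SAP, plus matching programming specifications. No new data are needed.

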8.8. Treatment Compliance

Study drug compliance will be assessed by counting returned used or unused prefilled syringes. A patient will be considered compliant with the dosing regimen if the patient received $\geq 75\%$ of the expected number of injections while enrolled in the study.

The formula to calculate the treatment compliance is the following:

$$\text{Treatment compliance (\%)} = 100 \times \frac{\text{Total not returned kit}}{\text{Total number of injections expected}}$$

Where according to the eCRF entry instruction, the "Total not returned kits" is equivalent to the "total used kits".

Treatment compliance will be listed for each period.

This document is confidential.

9. Efficacy

9.1. Statistical Hypotheses

The statistical hypothesis to be tested for the main estimand of the primary efficacy endpoint (Percentage of patients achieving EASI 75 at Week 16) are:

- $H_0: P_{Lebrikizumab} - P_{placebo} = 0$
- $H_1: P_{Lebrikizumab} - P_{placebo} \neq 0$,

where $P_{Lebrikizumab}$ refers to the true proportion of patients receiving lebrikizumab, and $P_{placebo}$ refers to the true proportion of patients receiving placebo that achieve EASI 75 at Week 16. The testing procedure will thus be 2-sided. Confirmatory testing is conducted using the main estimand of the primary efficacy endpoint.

For analyses related to the Maintenance Period, only descriptive analyses will be presented. No specific statistical hypotheses thus apply for the Maintenance Period.

9.2. Definitions for Efficacy Endpoints

For all efficacy endpoints where a derived categorisation is defined in this section, if the category is collected on the eCRF then it will be used in the analysis and will not be derived. Otherwise, the category will be derived based on the recorded (or imputed) measure.

This document is confidential.

Measure	Description	Variable	Derivation / Comment	Imputation Approach if Missing Components
Eczema Area and Severity Index (EASI)	
The EASI scoring system uses a defined process (Steps 1-5 below) to grade the severity of the signs of eczema and the extent affected.
 
The extent of disease (percentage of skin affected: 0 = 0%; 1 = 1-9%; 2 = 10-29%; 3 = 30-49%; 4 = 50-69%; 5 = 70-89%; 6 = 90-100%) and the severity of 4 clinical signs (erythema, edema/papulation, excoriation, and lichenification) each on a scale of 0 to 3 (0 = none, absent; 1 = mild; 2 = moderate; 3 = severe) at 4 body sites (head and neck, trunk, upper limbs, and lower limbs). Half scores are allowed between severities 1, 2 and 3. Each body site will have a score that ranges from 0 to 72, and the final EASI score will be obtained by weight-averaging these 4 scores. Hence, the final EASI score will range from 0 to 72 for each time point.
	EASI score	
Derive EASI region score for each of head and neck, trunk, upper limbs, and lower limbs as follows:
 $\text{EASI}_{\text{region}} = (\text{Erythema} + \text{edema/papulation} + \text{Excoriation} + \text{Lichenification}) * (\text{value from percentage involvement})$ 
where erythema, edema/papulation, excoriation, and lichenification are evaluated on a scale of 0 to 3 and value from percentage involvement is on a scale of 0 to 6.
 
Then total EASI score is as follows:
 $\text{EASI} = 0.1 \cdot \text{EASI}_{\text{head and neck}} + 0.3 \cdot \text{EASI}_{\text{trunk}} + 0.2 \cdot \text{EASI}_{\text{upper limbs}} + 0.4 \cdot \text{EASI}_{\text{lower limbs}}$	If value of percentage involvement is 0 for any region, then severity scores of that region could be missing. Otherwise missing if any component is missing.
		EASI 50	% Improvement in EASI score from baseline $\geq 50\%$: % change from baseline ≤ -50	Missing if baseline or observed value is missing.
		EASI 75	% Improvement in EASI score from baseline $\geq 75\%$: % change from baseline ≤ -75	Missing if baseline or observed value is missing.

This document is confidential.

Measure	Description	Variable	Derivation / Comment	Imputation Approach if Missing Components
		EASI 90	% Improvement in EASI score from baseline $\geq 90\%$: % change from baseline ≤ 90	Missing if baseline or observed value is missing.
		Time (in days) to EASI 50 (75) (90) up to week 16	Date of first time % change from baseline in EASI score ≥ 50 (75) (90) - date of W16 visit +1	If a patient has not experienced achievement of EASI 50 (75) (90) by completion or early discontinuation of Induction Period, the patient will be censored at the date of their last visit during Induction Period.
Investigator's Global Assessment (IGA)	The IGA is a static assessment and rates the severity of the patient's AD. The IGA is comprised of a 5-point scale ranging from 0 (clear) to 4 (severe) and a	IGA score	Single item. Range: 0 to 4 0 represents "clear" 4 represents "severe"	Single item, missing if missing.

This document is confidential.

Measure	Description	Variable	Derivation / Comment	Imputation Approach if Missing Components
	score is selected using descriptors that best describe the overall appearance of the lesions at a given time point.	IGA 0/1 with 2-point improvement	Observed score of 0 or 1 and change from baseline = -2	Missing if baseline or observed value is missing. Single item, missing if missing.
Body Surface Area (BSA)	The BSA assessment estimates the extent of disease or skin involvement with respect to AD and is expressed as a percentage of total body surface. BSA will be determined by the Investigator or designee using the patient palm = 1% rule	BSA score	BSA Total = BSAhead and neck + BSAtrunk + BSAupper extremities + BSAlower extremities	N/A – partial assessments cannot be saved.
		Change from baseline in BSA score	Change from baseline: observed BSA score – baseline BSA score	Missing if baseline or observed value is missing.
SCORing Atopic Dermatitis (SCORAD)		SCORAD score	SCORAD = A/5 + 7B/2 + C, where A is extent of disease, range 0-100 B is disease severity, range 0-18 C is subjective symptoms, range 0-20	Missing if component A or B or C is missing.

This document is confidential.

Measure	Description	Variable	Derivation / Comment	Imputation Approach if Missing Components
	
SCORAD is a validated clinical tool for assessing the extent and intensity of atopic dermatitis. There are 3 components to the assessment:
 
• The extent of AD is assessed as a percentage of each defined body area and reported as the sum of all areas, with a maximum score of 100% (assigned as "A" in the overall SCORAD calculation).• The severity of 6 specific symptoms of AD (redness, swelling, oozing/crusting, excoriation, skin thickening/lichenification, dryness) is assessed using the following scale: none (0), mild (1), moderate (2), or severe (3) (for a maximum of 18 total points, assigned as "B" in the overall SCORAD calculation). 
Subjective assessment of itch and of sleeplessness is recorded for each symptom by the patient or relative on a VAS, where 0 is no itch (or sleeplessness) and 10 is the worst imaginable itch (or sleeplessness), with a maximum possible score of 20 (assigned as "C" in the overall SCORAD calculation).
	Change from baseline in SCORAD score	Change from baseline: observed SCORAD score – baseline SCORAD score	Missing if baseline or observed value is missing.

This document is confidential.

Measure	Description	Variable	Derivation / Comment	Imputation Approach if Missing Components
Pruritus Numeric Rating Scale (NRS)	The Pruritus Numeric Rating Scale (NRS) is an 11-point scale used by patients to rate their worst itch severity over the past 24 hours with 0 indicating "No itch" and 10 indicating "Worst itch imaginable." Assessments will be recorded daily by the patient using an electronic diary.	Pruritus NRS prorated weekly mean score	The prorated weekly mean is based on previous 7 days. If the patient has at least one daily score, the weekly mean is the prorated average of daily scores within the given week. Single item; range 0-10.	Weekly mean score missing if the patient has no Pruritus-NRS responses within the week.
		4-point Pruritus improvement in Pruritus NRS prorated weekly mean score	Change from baseline in Pruritus NRS prorated weekly mean score ≤ 4	Missing if baseline is missing or observed value is missing.
Sleep-loss	Sleep-loss due to pruritus will be assessed by the patient. Patients rate their sleep based on a 5-point Likert scale [0 (not at all) to 4 (unable to sleep at all)]. Assessments will be recorded daily by the patient using an electronic diary.	Sleep-loss prorated weekly mean score	The prorated weekly mean is based on previous 7 days. If the patient has at least one daily score within the week, the weekly mean is the prorated average of daily scores within the given week. Single item; range 0 to 4.	Weekly mean score missing if the patient has no Sleep-loss responses within the week.
		Change from baseline in Sleep-loss prorated weekly mean score	Change from baseline: observed sleep loss prorated weekly mean score – baseline sleep loss score	Missing if baseline or observed value is missing.
Skin Pain NRS	The Skin Pain NRS is an 11-point scale used by patients to rate their worst pain over the past 24 hours with 0 indicating "No pain" and 10 indicating "Worst pain imaginable." Assessments will be recorded daily by the patient using an electronic diary.	Skin Pain NRS prorated weekly mean score	The prorated weekly mean is based on previous 7 days. If the patient has at least one daily score, the weekly mean is the prorated average of daily scores within the given week. Single item; range 0-10.	Weekly mean score missing if the patient has no Skin Pain NRS responses within the week

This document is confidential.

Measure	Description	Variable	Derivation / Comment	Imputation Approach if Missing Components
		Change from baseline	Change from baseline: observed Skin Pain NRS prorated weekly mean score – baseline Skin Pain NRS score	Missing if baseline or observed value is missing.
		4-point Skin Pain NRS improvement	Change from baseline in Skin Pain NRS prorated weekly mean score ≤4	Missing if baseline or observed value is missing.
Patient-Oriented Eczema Measure (POEM)	The POEM is a 7-item, validated, questionnaire used by the patient to assess disease symptoms over the last week. The patient is asked to respond to 7 questions on skin dryness, itching, flaking, cracking, sleep loss, bleeding and weeping. All 7 answers carry equal weight with a total possible score from 0 to 28 (answers scored as: No days=0; 1–2 days = 1; 3–4 days = 2; 5–8 days = 3; everyday = 4). A high score is indicative of a poor quality of life. POEM responses will be captured using an electronic diary and transferred into the clinical database.	POEM score	POEM total score: sum of questions 1 to 7, Range 0 to 28.	If a single question is left unanswered, then that question is scored as 0. If more than one question is unanswered, then the tool is not scored. If more than one response is selected, then the response with the highest score is used.
		Change from baseline in POEM score	Change from baseline: observed POEM score – baseline POEM score	Missing if baseline or observed value is missing.

This document is confidential.

Measure	Description	Variable	Derivation / Comment	Imputation Approach if Missing Components
Dermatology Life Quality Index (DLQI)	
DLQI is a validated, dermatology-specific, patient-reported measure that evaluates patient's health-related QoL. This questionnaire has 10 items that are grouped in 6 domains, including symptoms and feelings, daily activities, leisure, work and school, personal relationships, and treatment. The recall period of this scale is over the "last week". Response categories and corresponding scores are:
 
Very much = 3 A lot = 2 A little = 1 Not at all = 0 Not relevant = 0
 
Scores range from 0-30 with higher scores indicating greater impairment of quality of life. A DLQI total score of 0 to 1 is considered as having no effect on a patient's health-related QoL (Hongbo et al. 2005), and a 4-point change from baseline is considered as the minimal clinically important difference threshold (Khilji et al. 2002; Basra et al. 2008)
	DLQI total score	A DLQI total score is calculated by summing all 10 question responses and has a range of 0-30 (less to more impairment)	Score of 1 unanswered question = 0; If 2 or more questions are missing, the total score is missing. Note: #7B could be a valid missing while #7A is not "No." That is, #7 should be considered as 1 question.
		4-point improvement	Change from baseline ≤-4	Missing if baseline is missing or observed value is missing.
		DLQI total score and domain scores change from baseline	Calculated for each post-baseline assessment as: observed DLQI (total score or domain scores) – baseline DLQI (total score or domain scores)	Missing if baseline or observed value is missing
Children's Dermatology Life Quality Index (CDLQI)	
The CDLQI is designed to measure the impact of any skin disease on the lives of children. Patients ≤16 years will complete the CDLQI and should continue to complete the CDLQI for the duration of the study.
 
The scoring of each question is:
	CDLQI total score	A CDLQI total score is calculated by summing all 10 question responses and has a range of 0-30	Score of 1 unanswered question = 0; If 2 or more questions are missing, the total score is missing.
		4-point improvement	Change from baseline ≤-4	Missing if baseline is missing or observed value is missing.

This document is confidential.

Measure	Description	Variable	Derivation / Comment	Imputation Approach if Missing Components
	
 Very much = 3 Quite a lot = 2 Only a little = 1 Not at all = 0 Question unanswered = 0 Question 7: 'Prevented school' (text-only questionnaire) = 3 	CDLQI total score and domain scores change from baseline	Calculated for each post-baseline assessment as: observed CDLQI (total score or domain scores) – baseline CDLQI (total score or domain scores)	Missing if baseline or observed value is missing
Dermatology Life Quality Index-Relevant (DLQI-R)	The DLQI-Relevant (DLQI-R) is a recently developed scoring that adjusts the total score of the questionnaire for the number of 'not relevant' responses (NRRs) indicated by a patient.	Change from Baseline in DLQI-R total score by week up to Week 16	
The DLQI-R total score is calculated by summing the score of the 10 items. From here, the DLQI-R total score is calculated for each patient at each visit as the total DLQI score multiplied by $10/(10-NRR)$, where NRR is the number of not relevant responses for questions 3-10.
 
Change calculated for each post-baseline assessment as: observed DLQI-R total score – baseline DLQI-R total score
	Missing if baseline is missing or observed value is missing.
Topical Corticosteroids (TCS)	Topical Corticosteroids (TCS) Diary records patient's treatment of Atopic Dermatitis with a TCS and the areas of application. Assessments will be recorded daily up to W2, weekly from W2 to W16, and every 4 weeks from W16 onward by the patient using an electronic diary.	Proportion of free days from baseline to week 16	Proportion of TCS-free days is calculated as the total number of days in study from baseline to Week 16 where TCS were not used, divided by the total number of days in study from baseline to Week 16.	If patient does not complete study until Week 16 then total number of days will be capped at the date of the last assessment in study

This document is confidential.

Measure	Description	Variable	Derivation / Comment	Imputation Approach if Missing Components
		Time to TCS-free days from baseline to week 16	Time to TCS-free days is calculated as the time from baseline to first point where TCS are not used or Week 16 + 1, whichever is the earlier.	If patient does not complete study to Week 16 then censor at the date of the last assessment in study
RECAP	
RECAP is a seven-item questionnaire designed to capture the experience of eczema control in all ages and eczema severities.
 
Each of the seven questions in RECAP carries equal weight and is scored from 0 to 4 (total score of 0-28).
	Change from Baseline in RECAP by week up to Week 16	
The total RECAP score is calculated as the sum of all question scores.
 
Change calculated for each post-baseline assessment as:
 $\text{observed RECAP total score} - \text{baseline RECAP total score}$	
If one question is left unanswered this is scored 0 and the scores are summed and expressed as usual out of a maximum of 28.
 
If two or more questions are left unanswered the questionnaire is not scored.
 
If two or more response options are selected, the response option with the highest score should be recorded

World Health Organisation – Five Well-Being Index (WHO-5)	
The WHO-5 is a short, self-administered measure of well-being over the last two weeks. It consists of five positively worded items that are rated on 6-point Likert scale, ranging from 0 (at no time) to 5 (all of the time). The raw scores are transformed to a score from 0 to 100, with lower scores indicating worse well-being. A score of ≤50 indicates poor wellbeing and suggests further investigation into possible symptoms of depression. A score of 28 or below is indicative of depression.
	Change from Baseline WHO-5 by week up to Week 16	
Total raw score calculated as the sum of all raw scores. The total raw score (ranging from 0 to 25) is then multiplied by 4 to get the transformed total score between 0 and 100.
 
Change calculated for each post-baseline assessment as:
 $\text{observed WHO-5 transformed total score} - \text{baseline WHO-5 transformed total score}$	None

This document is confidential.

Measure	Description	Variable	Derivation / Comment	Imputation Approach if Missing Components
Treatment Satisfaction Questionnaire for Medication-9 items (TSQM-9)	Version 9 of the TSQM consists of 9 items that results in three specific domains: Effectiveness, Convenience, and one global scale item, Global Satisfaction. Scores for each domain are computed by adding the TSQM items in each domain and then transforming the composite score into a value ranging from 0 to 100.	EFFECTIVENESS	$\frac{((\text{Item 1} + \text{Item 2} + \text{Item 3}) - 3)}{18} * 100$	If one item is missing $\frac{((\text{Sum}(\text{Item 1?} + \text{Item 2?} + \text{Item 3?})) - 2)}{12} * 100$
		CONVENIENCE	$\frac{((\text{Sum}(\text{Item 9 to Item 11}) - 3)}{18} * 100$	If one item is missing $\frac{((\text{Sum}(\text{Item 9? to Item 11?})) - 2)}{12} * 100$
		GLOBAL SATISFACTION	$\frac{((\text{Sum}(\text{Item 12 to Item 14}) - 3)}{14} * 100$	If either Item 12 or 13 is missing $\frac{((\text{Sum}(\text{Item 12? to Item 14?})) - 2)}{10} * 100$ If Item 14 is missing $\frac{((\text{Sum}(\text{Item 12 and Item 13})) - 2)}{8} * 100$

Abbreviations: eCOA = electronic clinical outcome assessment

